10.4. Demographic and Other Baseline Characteristics

The safety population will be used in summaries of demographic and baseline data. No statistical testing will be used to compare treatment groups for different baseline characteristics.

10.4.1. Demographics

Demographic variables collected at Screening; sex, age, ethnicity, race, height (cm), weight (kg) and body mass index (BMI) will be summarised by treatment group and across all participants.

Age at screening and BMI are recorded in the database and do not need require derivation.

10.4.2. Substance Use History and Recreational Drugs of Misuse

Substance use history and any recreational drug misuse will be collected at screening and listed for all participants.

10.4.3. Reproductive Status and Contraceptive Use

The reproductive status and use of contraception will be collected at screening and listed for all participants.

10.4.4. Medical History

Medical history data will be coded using MedDRA, Version 25.0 (March 2022) and all data will be listed.

10.5. Prior and Concomitant Medications

Prior and concomitant medication terms will be coded using the World Health Organisation (WHO) Drug Dictionary Enhanced (WHO Drug Global, Version March 1 2022). A medication will be assigned as being prior to inoculation based on the start and stop dates of the medication and the date of challenge agent inoculation. If the medication stop date is before the inoculation date, the medication will be assigned as being prior to inoculation. A medication will be assigned as being prior to IMP or concomitant with IMP, based on the start and stop dates of the medication and the IMP. If the medication stop date is before the IMP start date and after the date of inoculation, the medication will be assigned as being prior to IMP. In all other situations, the medication will be assigned as being concomitant with IMP. If a participant has separate periods of taking specific medications, then that medication is only counted once within the specific period of observation (i.e., prior, or concomitant) where it is taken.

Note: Start and Stop times will not be used for determining if a medication is concomitant or not.

Concomitant medications up to the Day 28 visit will be summarised, using the Safety Population, by treatment group (and across all participants), Drug Class (L3) and preferred base name (01001). If Level 3 is missing for a medication then Level 2 will be used instead.

Prior medications will not be summarised but these will be listed.

10.6. IMP Exposure and Compliance

The study consists of 10 doses of IMP administered twice daily for 5 consecutive days. The expected number of doses will be calculated using the start/stop dates and times for each participant. Compliance with IMP will be derived as:

$$(\text{number of doses received}/\text{number of doses expected}) * 100.$$

Compliance will be summarised by treatment group and for all participants as a continuous variable and will also be summarised categorically in the following classifications: <80%, 80-120% and >120%.

10.7. Statistical Analysis

All efficacy analyses will be based on the ITT-I population as the primary analysis. Where the populations differ to ITT-I population by 1 participant within a treatment group, the primary and selected secondary analyses will be repeated for the ITT-A, ITT-B, ITT and PP populations. This will be reviewed and documented at the BDRM.

10.7.1. Primary Endpoint

10.7.1.1 Main Analysis

The primary endpoint is the AUC of RSV-A Memphis 37b viral load measured in nasal washes by qRT-PCR, from the last measurement collected prior to the first administration of IMP until the last measurement collected up to the morning of Day 12 (Quarantine discharge). The viral load data will be supplied as \log_{10} copies/mL and will be used for this main analysis and to calculate the AUC using the trapezoidal rule [1].

The AUC will be summarised for RV299 and placebo using descriptive statistics and an ANCOVA with treatment group as a main effect and the baseline value as a covariate. The baseline value will be the qRT-PCR viral load value from the last measurement collected prior to the first administration of IMP. The treatment comparison will be presented, including the LS mean treatment difference with the corresponding two-sided 95% confidence interval and p-value. The equivalent Wilcoxon rank-sum tests will be provided in place of the ANCOVA where the assumptions of the parametric test are not met.

As nasal washes are scheduled to be taken twice daily for Days 2 to 11 (and once on Day 12), in order to calculate the AUC, the actual time that the assessment was collected will be used within the AUC calculation. The AUC calculation will be based on the available non-missing assessment values between the start and end of the defined AUC time period. However, for an AUC to be derived, a participant should have at least one non-missing data recording at the start of the AUC period (e.g. date of first administration of IMP) and also at the end of the AUC time period (e.g. Day 12). In addition, the participant should have at least 1 non-missing data recording on each day between the start and end of the defined AUC time period (i.e. at least 1 out of the 2 possible assessments on each Day)). Any missing data will be reviewed at the BDRM, for its potential impact on this endpoint, and any decisions to exclude participants as a result of these criteria will be documented in the BDRM minutes. For the reporting of AUC, where appropriate, qRT-PCR values that are 'Not Detected' or 'Detected' will be re-assigned using the substitution values shown in the table in Appendix 15.1.

As well as a descriptive statistics summary of AUC values, the mean qRT-PCR values (+/- 1 Standard Error (SE)) will be displayed graphically by day (relative to first dose of IMP) and assessment, and treatment group. In order to calculate the time point that each assessment will be presented against,

a relative day and relative assessment will be assigned. The last qRT-PCR measurement collected prior to the first dose of IMP will be assigned to be the value at time point 1, while measurements collected on subsequent assessments and days will be assigned to subsequent time points in sequential order (i.e. time point 2, 3 and so on). Time point 1 will be presented against Day 0 assessment 1, while subsequent time points will be presented against Day 0 assessment 2, Day 1 assessment 1, and so on.

[Line graph: y-axis = mean of qRT-PCR (\log_{10} copies/mL), x-axis = day relative to dosing, one line for each treatment on same plot].

A boxplot will also be presented by day (relative to first dose of IMP) and assessment, plotting the median and mean qRT-PCT values for each treatment group, with the corresponding summary statistics.

[Box plot: y-axis = mean of qRT-PCR (\log_{10} copies/mL), x-axis = day relative to dosing, one box-and-whisker for each day, with each treatment panelled with RV299 at the top and placebo below].

Note: For multiple assessments taken within each day, so as to be able to plot mean values across participants (within a treatment group) by day, the actual collection time point (which may differ across participants) will not be used. Rather all first and second assessments will have mean values separately calculated and plotted as two means within each day. These two means will be shown equally spaced along the x-axis within the graph.

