6. STUDY DESIGN

6.1. Summary of Study Design

This is a single-centre, randomised, double-blind, placebo-controlled, proof-of-concept study in healthy adult male and female participants from 18 to 55 years of age, inclusive. The primary goal of this Phase 1b study is to assess the antiviral activity of RV299 against RSV in the viral challenge model. In addition, the safety, tolerability, and PK of RV299 will be assessed.

A total of 80 participants is planned to be enrolled in this study: 40 participants on RV299 and 40 participants on placebo.

The study is divided into the following study phases:

- Screening phase: from Day -90 to Day-3 pre-human viral challenge (HVC). Historical generic screening data collected through the hVIVO generic screening process may be transferred to this study after the study-specific consent form has been signed by the participant.
- Inpatient phase: Participants will be resident in the quarantine unit for approximately 15 days (from Day -2 to Day 12). Procedures will include:
 - Pre-HVC:
 - Admission to quarantine unit on Day -2/-1.
 - Baseline assessments will be conducted as per Schedule of Events (SoE) up to Day 0, pre-challenge.
 - HVC: RSV-A Memphis 37b virus inoculation on Day 0.
 - Post-HVC:
 - Randomisation to receive RV299 or matched placebo.
 - Administration of IMP (RV299/placebo). Each participant will receive IMP twice daily (~12 hours interval) for 5 consecutive days:
 - IMP dosing to start on confirmation of RSV infection, i.e., after a positive result by qualitative integrative cycler polymerase chain reaction (qicPCR). The qicPCR of nasal wash will be performed twice daily on Days 2-5 (Day 5 morning only), or until a positive result is received, whichever is sooner. The earliest start of IMP dosing will be in the evening of Day 2 post-HVC (IMP will be initiated 12 hours \pm 1-hour post nasal wash confirmation of infection)
 - OR
 - IMP would start in the evening of Day 5, if no positive result obtained by qicPCR
 - Day 1 onwards and each day study assessments will be conducted as per SoE.
 - Participants will be discharged from the quarantine unit on Day 12 (or may remain longer at the discretion of the principal investigator [PI]/investigator).
- Outpatient phase:
 - Final visit: Day 28 (\pm 3 days).

The overall study design is depicted in

Table 1.

Table 1: Study Schematic: On-study Participant Progression

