10. PLANNED STATISTICAL METHODS

10.1. Statistical Considerations

10.1.1. General Definitions

In all applicable summary/analysis presentations of safety endpoints, Baseline is defined as the last non-missing assessment value for a participant, for that particular parameter, that is prior to inoculation of challenge virus, unless over-ruled after review of data at the BDRM or otherwise stated in the appropriate endpoint sections below, whatever the reason for that assessment (e.g. if it is a repeat assessment, then it should be used as the baseline). For efficacy endpoints, the baseline definition is as per the appropriate endpoint sections below. For the derivation of most efficacy endpoints, the first assessment to be used should be the assessment that was taken at the time of first administration of IMP. For example, if a participant was first dosed on the morning of Day 3 then the first qRT-PCR value to be used in the AUC of qRT-PCR viral load (from time of first administration) derivation should be the Day 3 morning assessment. For endpoints using symptom diary card data, the definition of baseline will be defined in greater detail within the appropriate sections of the SAP.

A participant will be classed as infected, and therefore randomised to be dosed, when they have a positive result for RSV-A Memphis 37b by qualitative integrative cycler polymerase chain reaction (qicPCR) from nasal wash sample. IMP administration will be initiated 12 hours after a positive result. However, if a participant remains uninfected, IMP administration will begin on the evening of Day 5.

For participants that extend their time in quarantine beyond Day 12, the additional assessments beyond Day 12 will be listed only, and will not be used for the derivation of any efficacy endpoints. For the avoidance of doubt, the assessment performed on the morning of Day 12 will be the final assessment used for all analyses and summaries for all participants. If additional assessments are taken on Day 12, then they will be listed only. However, the use of data beyond the morning of Day 12 will be discussed at the BDRM.

A participant will be considered to have completed the study after their attendance at the last planned study visit (Day 28 (\pm 3 days)), or the last unscheduled visit (if any occur), as applicable.

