10.7.2.5 Nasal Discharge Endpoints

Total Weight of Mucus Produced Starting at Initial Administration of IMP up to Planned Discharge from Quarantine

Total weight of nasal mucus (grams) will be calculated as the sum of mucus weights taken from the assessment at the time of the first administration of IMP (can be prior to or after dosing, depending on whether dosed in the morning or evening) to morning of Day 12 (Quarantine discharge). Total mucus weight will be summarised by treatment group and will include the change from baseline, where baseline is the last assessment recorded prior to receiving a positive result for RSV by qicPCR. For participants who did not receive a positive result, the final assessment prior to the first administration of IMP will be defined as the baseline score.

Total Number of Tissues Used by Participants Starting At Initial Administration of IMP up to Planned Discharge from Quarantine

Total number of tissues will be counted from the assessment at the time of the first dose of IMP (can be prior to or after dosing, depending on whether dosed in the morning or evening) to morning of Day 12 (Quarantine discharge). This count will be summarised by treatment group and will include the change from baseline, where baseline is the last assessment recorded prior to receiving a positive result for RSV by qicPCR. For participants who did not receive a positive result, the final assessment prior to the first administration of IMP will be defined as the baseline score.

CCI

[REDACTED]

[REDACTED]

[REDACTED]

[REDACTED]

CCI

CCI

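### The primary AUC window varies from 6.5 to 9.5 days with the pre-randomisation dosing slot, but the ANCOVA does not adjust for slot; precision may be lost, validity is not

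*SAP*

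**What the plan says.** SAP 10.7.1.1 defines the primary AUC "from the last measurement collected prior to the first administration of IMP until the last measurement collected up to the morning of Day 12", by the trapezoidal rule on log10 values. It is not divided by the length of the window. The analysis is "an ANCOVA with treatment group as a main effect and the baseline value as a covariate"; SAP 10.1.4 and the footnote to Table 14.2.1.1 give the same two terms. If the parametric assumptions fail, a Wilcoxon rank-sum test replaces the ANCOVA.

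The window starts when dosing starts. SAP 6.1 states "The earliest start of IMP dosing will be in the evening of Day 2 post-HVC" and, at the other end, "IMP would start in the evening of Day 5, if no positive result obtained by qicPCR". SAP 10.1.1 says that a positive qicPCR leads to randomisation and that "IMP administration will be initiated 12 hours after a positive result". Its example is a participant first dosed on the morning of Day 3, for whom the first value in the AUC "derivation should be the Day 3 morning assessment".

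Neither Protocol 6.3 nor SAP 6.2 describes stratification by start slot.

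SAP 10.7.1.2 adds two fixed-window sensitivity analyses: 6.5 days from the last pre-dose wash, and Day 2 morning to Day 12 morning. The table list carries both over to the culture and symptom AUCs. All use the same testing methods as the main analysis.

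**The concern.** Slot determines how long the primary outcome can accumulate, and it may also carry information about the course of infection. It is settled before allocation, so adjusting for it is safe. Without it in the model, any AUC variation due to slot goes into the residual, and a chance difference in slot between arms stays in the estimate.

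The primary population is small: Protocol 2.3 expects 65% to 85% of challenged participants to become infected, which is about 52 to 68 of 80. Baseline viral load is probably a weak stand-in for slot, because most participants are sampled about 12 hours after first testing positive, whatever their slot.

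**Working it through.** **Inputs.** First dose from Day 2 pm to Day 5 pm (SAP 6.1). AUC end at Day 12 am (SAP 10.7.1.1). Sampling: "nasal washes are scheduled to be taken twice daily for Days 2 to 11 (and once on Day 12". Planned N 80, allocated 1:1. Infection rate 65% to 85% (Protocol 2.3). Two-sided 5% tests (SAP 10.1.4).

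**The SAP's own figure.** SAP 10.7.1.2 gives 6.5 days and 14 assessments for a Day 5 evening start. Length: 12.0 − 5.5 = 6.5 days. Washes: 1 (Day 5 pm) + 2 × 6 (Days 6 to 11) + 1 (Day 12 am) = 14. Both reproduce.

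**All slots.** The qicPCR is done twice daily on Days 2 to 4 and once on Day 5, which is seven washes. With a 12-hour lag these give seven slots. Length = 12.0 − slot; washes = 2 × length + 1.

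| First dose | Window (days) | Hours | Washes |
|---|---|---|---|
| Day 2 pm | 9.5 | 228 | 20 |
| Day 3 am | 9.0 | 216 | 19 |
| Day 3 pm | 8.5 | 204 | 18 |
| Day 4 am | 8.0 | 192 | 17 |
| Day 4 pm | 7.5 | 180 | 16 |
| Day 5 am | 7.0 | 168 | 15 |
| Day 5 pm | 6.5 | 156 | 14 |

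The longest window is 9.5 / 6.5 = 1.46 times the shortest. If the wash in the dosing slot is missing or taken after dosing, the start moves back 12 hours and the range becomes 7.0 to 10.0 days.

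**Chance imbalance.** The documents give no distribution of slots. Under three assumed ones (equal, centred on Day 4 am, weighted to late slots) the SD of window length is 0.8 to 1.0 day. Infected participants per arm: 40 × 0.65 = 26 to 40 × 0.85 = 34. The SD of the between-arm difference in mean window is SD × √(2/n), from 0.8 × √(2/34) = 0.19 to 1.0 × √(2/26) = 0.28 day.

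**Effect on precision.** If slot has partial R² = r given treatment and baseline, residual variance is multiplied by (1 − r). For an effect with 80% power unadjusted, adjusted power is Φ(2.802/√(1 − r) − 1.960). This does not depend on n.

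| r | Power | n per arm equivalent to 30 unadjusted |
|---|---|---|
| 0 | 0.800 | 30.0 |
| 0.02 | 0.808 | 29.4 |
| 0.05 | 0.820 | 28.5 |
| 0.10 | 0.840 | 27.0 |
| 0.12 | 0.848 | 26.4 |

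**Plausible r.** The documents give no SD or shedding curve, so r comes from simulated curves under assumed kinetics:

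- Clearance timed from infection onset and complete within about 6.5 days of dosing: r about 0 to 0.01.
- Clearance timed from onset, longer shedding: r about 0.01 to 0.04.
- Clearance timed from inoculation: r about 0.06 to 0.12.

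Making 60% of the Day 5 pm slot low shedders who were never qicPCR-positive gave 0.001 to 0.042 (onset-timed) and 0.059 to 0.100 (inoculation-timed). With clearance timed from inoculation, slot still explained about 3 to 12% of residual variance in the fixed 6.5-day AUC. In no scenario did adjustment cost meaningful precision.

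**The case against.** The strongest reply is that choosing one more prognostic covariate is a judgement, and that the SAP has already dealt with unequal windows. Much of this stands. Both fixed-window analyses equalise length, and they extend to the culture and symptom AUCs. What they leave open is that they are secondary and keep the two-term model. The Day 2 to Day 12 version also brings pre-dose viral load, which treatment cannot affect, into the AUC of later starters.

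Four stronger readings are tempting and are not supported:

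- **Bias.** A reader might infer that unequal windows bias the comparison. Slot is set before 1:1 allocation, so only chance imbalance arises, and the unadjusted standard error already allows for it.
- **AUCs differing by 1.46.** That is the ratio of window lengths. It would carry over to AUC only if shedding stayed flat to Day 12. SAP Appendix 15.1 scores Not Detected as 0, so days after clearance add nothing.
- **A demonstrated loss of power.** The sample-size rationale is not visible in the public text, so it cannot be seen whether the planning SD already included this variation. Default Day 5 pm starters who never meet the infection criterion also fall outside ITT-I, which thins the short-window end.
- **The nasal discharge totals.** SAP 10.7.2.5 says "Total weight of nasal mucus (grams) will be calculated as the sum of mucus weights", so these too accumulate over unequal periods. But mucus weight and tissue count have no inferential test (Protocol Table 9-2), and residual error is not at issue.

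**Conclusion.** The point holds as one of precision. The 6.5 to 9.5 day range, the pre-randomisation status of slot and its absence from the model all follow directly from the documents. The size of the gain does not. Under assumed kinetics it is about 0 to 12% of residual variance, or 80% power becoming about 80 to 85%. It is near zero if PCR shedding ends within 6.5 days of dosing and largest if clearance runs on a clock from inoculation. The planned ANCOVA remains a valid test at its nominal level. The change is worth making because slot is known for everyone and adjustment costs almost nothing, not because a large loss has been shown.

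**What to change.** Before unblinding, add the qicPCR-determined first-dose slot (Day 2 pm to Day 5 pm) as a covariate in the primary ANCOVA and in the other from-dose AUC models (culture and symptom). Use the assigned slot and not the actual dosing time, which follows randomisation. Add an indicator for participants never qicPCR-positive who start by default on Day 5 pm; otherwise that slot pools them with those first positive on the Day 5 morning wash. SAP 10.1.4 already allows endpoint-specific covariates. If the data are already unblinded, report the adjusted model as a labelled post hoc analysis.

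The cost is one or two degrees of freedom: with 52 infected participants, residual df falls from 52 − 3 = 49 to 48 or 47. The term has no effect where the Wilcoxon test is used, and the programming note to the symptom AUC tables expects that fallback there.

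AUC divided by window length should be supportive at most. It is a different quantity, because a longer window after clearance lowers the average. Mucus weight and tissue count per day are an optional display.
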